5.2.5.2 Sum of Diameters

Per RECIST Version 1.1, tumor burden is measured by the SOD of all target lesions (longest diameter for non-nodal lesions, short axis for nodal lesions) at each tumor assessment.

5.3 Exploratory Endpoints

5.3.1 Time to Response per Investigator Assessment

Time to response (TTR) per RECIST Version 1.1 by investigator assessment will be calculated as the time from the first dose of study drug to the first documented objective response (CR or PR that is subsequently confirmed) per investigator assessment. TTR will only be calculated for subjects who achieved a confirmed CR or PR per investigator assessment. The primary analysis population for DCR is RES who achieved a confirmed CR or PR.

5.3.2 Response Related Endpoints per RECIST Version 1.1 by Blinded Independent Central Review

Imaging scans for a cohort may be read at the independent review facility when the minimum number of responders per investigator assessment (subjects with confirmed CR or PR) at stage 1 are met based on the 2-stage BOP2 design. Central images may also be read in certain circumstances as determined by the sponsor. The following response related endpoints will be derived similarly as the corresponding endpoint per investigator assessment, except that timepoint tumor response per independent central review will be used.

- Confirmed ORR per BICR
- DOR per BICR
- DCR per BICR
- PFS per BICR
- BOR per BICR
- TTR per BICR

5.3.3 iRECIST Efficacy Endpoints by Investigator Assessment

For Cohort 9, additional endpoints of iBOR, iORR, iDCR, iPFS, and iDOR will be analyzed based on iRECIST guidelines.

5.3.3.1 Best Overall Response per iRECIST (iBOR)

iBOR is determined based on all available timepoint tumor response data for a participant. Participants will be classified by best response on study in order of iCR, iPR, iSD, iUPD, iCPD, and NE as outlined in iRECIST criteria. For best overall response of iSD, iSD must be documented as present at least 7 weeks after first dose. For confirmed iCR or iPR, response must be confirmed at a subsequent timepoint that is at least 4 weeks from the first documentation of iCR or iPR. Confirmatory scan for iUPD must occur at least 4 weeks after the date that iUPD was first observed but no longer than 8 weeks.

5.3.3.2 iORR

iORR with confirmed response is defined as the proportion of participants whose iBOR is a confirmed iCR or confirmed iPR per iRECIST as assessed by investigator. Definition of iBOR is specified in Section 5.3.3.1.

5.3.3.3 iDCR

iDCR with confirmed response is defined as the proportion of participants whose iBOR is a confirmed iCR or confirmed iPR or iSD per iRECIST as assessed by investigator. Definition of iBOR is specified in Section 5.3.3.1.

5.3.3.4 iPFS

iPFS is defined as the time from the start of study treatment to the first iUPD which is subsequently confirmed per iRECIST (iCPD) as assessed by investigator or death due to any cause whichever comes first.

Table 1 iPFS Definition

Situation	Date of Event or Censor	Outcome
No evaluable post-baseline imaging assessments, no death	Date of first dose (Day 1)	Censor
Death before first documented iUPD and subsequent anticancer therapy and not after two or more consecutive missed assessments	Date of death	Event
Documented iCPD (confirmed progression) before subsequent anticancer therapy and not after two or more consecutive missed assessments	Date of the initial iUPD that is subsequently confirmed	Event
Documented iUPD and the subject is not clinically stable to continue on treatment	Date of iUPD	Event
Documented iUPD without subsequent scans before subsequent anticancer therapy and the subject is no longer in response follow-up	Date of iUPD	Event
Documented iUPD and all subsequent assessments are iUPD(s) or NE(s) and the subject is no longer in response follow-up	Date of iUPD	Event
None of the above and subsequent anticancer therapy started	Date of last disease assessment prior to start of subsequent anticancer therapy	Censor
Death or documented iUPD right after two or more consecutive missed disease assessments	Date of last disease assessment prior to the missed visits	Censor
None of the above	Date of last disease assessment on study	Censor

iPFS = Date of Event or Censor – Date of First Dose +1

New anti-cancer therapy includes therapies captured on new anti-cancer therapy eCRF and new radiation therapy eCRF.

For a participant who is censored, the last evaluable radiological tumor assessment refers to the participant's last radiological tumor assessment where the response is not NE.

When a cutoff date is applied to iPFS analysis, tumor assessment, death and new anti-cancer treatment occurring after the cutoff date will be excluded from the analysis.

5.3.3.5 iDOR

iDOR is defined as the time from the date of first documented response (iCR or iPR that is subsequently confirmed) as assessed by investigator to the date of first documented radiological disease progression per iRECIST or death due to any cause whichever occurs

first. iDOR will only be calculated for subjects achieving a confirmed iCR or iPR. The same censoring rules as described in Table 1 for iPFS will be applied for iDOR.

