7.1.2.2.2 Progressive Disease

PD of nontarget lesions is defined as unequivocal progression of existing nontarget lesions or the appearance of 1 or more new lesions.

7.1.3 iRECIST Assessment

Response will also be assessed using iRECIST guidelines [Seymour et al, 2017] for Cohort 9. Immunotherapeutics may result in infiltration of immune cells leading to transient increase in the size in malignant lesions, or undetectable lesions becoming detectable. The criteria are identical to those of RECIST Version 1.1 in many respects but have been adapted to account for instances where an increase in tumor burden, or the appearance of new lesions, does not reflect true tumor progression.

Key differences are described below. All responses defined using iRECIST guidelines are designated with a prefix. iRECIST time point and best responses will be recorded separately.

Confirming Disease Progression

Unlike RECIST Version 1.1, the iRECIST guidelines require the confirmation of progression and uses the terms iUPD (unconfirmed immune progressive disease) and iCPD (confirmed immune progressive disease). Confirmatory scans should be performed at the next scheduled disease assessment (6 weeks \pm 1 week). iCPD is confirmed if further increase in tumor burden, compared to the last assessment, is seen as evidenced by 1 or more of the following:

- Continued increase in tumor burden (from iUPD) where RECIST Version 1.1 definitions of progression had been met (from nadir) in target, nontarget disease or new lesions
- Progression in target disease worsens with an increase of at least 5 mm in the absolute value of the sum
- Continued unequivocal progression in nontarget disease with an increase in tumor burden
- Increase in size of previously identified new lesion (s) (an increase of at least 5 mm in the absolute value of the sum of those considered to be target new lesions) or additional new lesions
- RECIST Version 1.1 criteria are met in lesions types (target and/or nontarget and/or new lesions) where progression was not previously identified, including the appearance of additional new lesions

If iUPD is not confirmed at the next assessment, then the appropriate response will be assigned (iUPD if the criteria are still met, but no worsening, or iSD [immune stable disease], iPR [immune partial response] or iCR [immune complete response] if those criteria are met compared to baseline). Please refer to the iRECIST guidelines [Seymour et al, 2017] for more details.

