9.4.3.3 Time to Response

Time to response (TTR) will be calculated as the time from the first dose of study drug to the first documentation of objective response (CR or PR that is subsequently confirmed) per RECIST Version 1.1. TTR will only be calculated for subjects achieving a confirmed CR or PR. TTR will be summarized by descriptive statistics.

9.4.3.4 iRECIST Efficacy Endpoints

For Cohort 9, separate endpoints of iORR, iDCR, iDOR, and iPFS will be analyzed based on iRECIST guidelines.

Confirmed iORR is defined as the proportion of subjects whose BOR is a confirmed iCR or iPR according to iRECIST as assessed by investigator. The confirmed iORR for cohort 9 will be calculated and its 95% confidence interval will be constructed by the Clopper-Pearson method. The analysis set for confirmed iORR is RES.

iDCR with confirmed response is defined as the proportion of subjects whose BOR is confirmed iCR or confirmed iPR or iSD per iRECIST as assessed by investigator. iDCR for cohort 9 will be calculated and its 95% confidence interval will be constructed by Clopper-Pearson method.

iDOR is defined as the time from the date of first documented response (iCR or iPR whichever is first recorded) to the date of first documented radiological disease progression per iRECIST as assessed by investigator or death due to any cause, whichever occurs first. iDOR will only be calculated for subjects achieving a confirmed iCR or iPR. iDOR will be analyzed using Kaplan-Meier methodology and Kaplan-Meier plots will be provided. The median iDOR and its 2-sided 95% CI will be calculated.

iPFS is defined as the time from start of study treatment to first documentation of radiological disease progression per iRECIST as assessed by investigator or death due to any cause, whichever comes first. iPFS will be analyzed using Kaplan-Meier methodology and Kaplan-Meier plots will be provided. The median iPFS and its 2-sided 95% CI will be calculated.

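### SAP Table 1 censors a death that follows an iUPD which has reverted to iSD, iPR or iCR, although iPFS is defined to count death from any cause (cohort 9, exploratory endpoints)

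*SAP*

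**What the plan says.** SAP section 5.3.3.4 defines iPFS as running from the start of treatment to the first iUPD that is later confirmed, "as assessed by investigator or death due to any cause whichever comes first". Protocol section 9.4.3.4 likewise ends iPFS at progression "per iRECIST as assessed by investigator or death due to any cause, whichever comes first". Neither text makes death conditional on there having been no earlier iUPD.

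Table 1 in the same SAP section turns the definition into nine situations. Only one is an event dated at death: "Death before first documented iUPD and subsequent anticancer therapy and not after two or more consecutive missed assessments". The other event rows are dated at an iUPD. They cover:
- confirmed progression;
- an iUPD in a subject too unstable to continue treatment;
- an iUPD with no later scan;
- an iUPD followed only by iUPD or NE.

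The last two of these also require that response follow-up has ended. Anyone left over is censored at "Date of last disease assessment on study".

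SAP section 5.3.3.5 adds for iDOR: "The same censoring rules as described in Table 1 for iPFS will be applied for iDOR".

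Protocol section 7.1.3 allows an iUPD to be reversed: "If iUPD is not confirmed at the next assessment, then the appropriate response will be assigned". The responses that may be assigned include iSD, iPR and iCR.

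**The concern.** An iUPD that later reverts is the pattern iRECIST was added to accommodate in cohort 9. The protocol lets clinically stable subjects stay on treatment through it. Once such a subject has had any iUPD, the death row is closed to them for good, even though that iUPD no longer counts as progression. If they then die while their latest scan shows no progression, the table records them as alive and progression-free at that scan.

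This is informative censoring: follow-up for the endpoint ends because the subject died. It removes an event that the definition requires, so it favours the treatment.

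**Working it through.** The plan states no event count, power or estimate for iPFS, so there is no figure to reproduce. The check applies Table 1 to individual histories.

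**Inputs.** Cohort 9 scans fall at week 9 and then every 6 weeks (protocol section 4.1), so at weeks 9, 15, 21 and 27. The planned cohort size is 40 (SAP section 3).

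**One history, row by row.** iUPD at week 9, iSD at week 15, iPR at week 21, death at week 24, no new therapy, no missed scan, clinically stable throughout.

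1. No post-baseline imaging and no death: not met.
2. Death before the first documented iUPD: not met, since week 24 is after week 9.
3. "Documented iCPD (confirmed progression) before subsequent anticancer therapy and not after two or more consecutive missed assessments": not met, since progression was never confirmed.
4. iUPD and not clinically stable: not met.
5. iUPD with no later scan: not met, since scans exist at weeks 15 and 21.
6. iUPD followed only by iUPD or NE: not met, since later scans are iSD and iPR.
7. New anticancer therapy: not met.
8. Death or iUPD right after two or more missed assessments: not met.
9. Residual row: applies. Censored at week 21.

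Under the definition in section 5.3.3.4, the same subject has an event at week 24.

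**Seven histories, with Table 1 as written and with the death row reworded as under the fix.**

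| History (weeks) | As written | Reworded |
|---|---|---|
| A: no iUPD; death 24 | Event 24 | Event 24 |
| B: iUPD 9, iSD 15, iPR 21; death 24 | **Censored 21** | **Event 24** |
| C: iUPD 9, iSD 15, iSD 21; death 24 | **Censored 21** | **Event 24** |
| D: iUPD 9, no later scan; death 12 | Event 9 | Event 9 |
| E: iUPD 9, iUPD 15, NE 21; death 24 | Event 9 | Event 9 |
| F: iUPD 9, iSD 15, iUPD 21; death 24 | Event 21 | Event 21 |
| G: iUPD 9, iSD 15, iUPD 21, iCPD 27 | Event 21 | Event 21 |

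Only B and C change. History F is an event as written only if row 5 is read as applying to the second iUPD.

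**iDOR.** Take iUPD at week 9, iPR at weeks 15 and 21, and death at week 24. The two iPRs are 6 weeks apart, so the response is confirmed under the 4-week rule in SAP section 5.3.3.1, and iDOR starts at week 15. Applying Table 1 unchanged, the death still follows the first documented iUPD, so iDOR is censored at week 21. Section 5.3.3.5 itself ends iDOR at death from any cause.

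**Size.** If n subjects are at risk at the date of death, counting the death multiplies the Kaplan-Meier estimate by 1 − 1/n; censoring drops that factor. With n at its maximum of 40, the factor is 1 − 1/40 = 0.975, and it is further below 1 when fewer remain at risk. As a share of the cohort, for assumed numbers of affected subjects: 0/40 = 0%, 1/40 = 2.5%, 2/40 = 5%, 4/40 = 10%.

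**The case against.** The strongest reply is that the intent is plain. The sentence above the table speaks of a confirmed iUPD or any death, so a programmer might read the death row's iUPD as one that is later confirmed, which would close the gap. But the next row dates its event at the initial iUPD that goes on to be confirmed. The table therefore draws that distinction where it wants it, and the death row does not. The SAP revision log (version 4.0) mentions derivations held in the ADaM specifications. Those are not available here, and the log refers only to missed visits.

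A second reply is that the affected group is narrow. This stands. The subject must have a reverted iUPD, a non-progressing last scan, no later qualifying iUPD or iCPD, no new therapy and fewer than two consecutive missed scans, and must then die. With scans every 6 weeks, the window is usually one scan interval.

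A third reply is that iPFS and iDOR are exploratory, descriptive and confined to cohort 9, with no hypothesis or decision rule attached. This also stands. It limits the weight of the point but does not make the table consistent with its definition.

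A reader might infer two stronger points that the documents do not support:
- **That every death after an iUPD is lost.** Histories D and E show otherwise: those subjects have events, dated at the iUPD.
- **That the error inflates a planned contrast of iPFS with RECIST PFS.** No such contrast is planned. Protocol section 9.4.3.4 presents these as separate endpoints, and SAP section 6.4.3.3 only repeats the RECIST summaries.

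**Conclusion.** The point holds as a contradiction inside SAP section 5.3.3.4: the definition counts death from any cause, and the table censors one class of deaths. Table 1 gives a definite result for these subjects, and that result is wrong under the definition. It is therefore more than missing detail. For each affected subject the iPFS curve is too high from the date of death onward, and iDOR is affected in the same way where an iUPD blocks the death row.

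The number affected is not in the documents. It could be 0, and 1 to 4 of 40 (2.5% to 10%) is an assumed range shown for scale. The row-by-row result rests on reading the death row literally and on no correction existing in programming specifications that are not available here.

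Confirmed ORR, RECIST PFS and DOR, and OS are not touched: SAP sections 5.2.1, 5.2.3 and 5.2.4 place no iUPD condition on death. The point is worth correcting before analysis but does not bear on the primary conclusion for cohort 9.

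**What to change.** Replace the death row of SAP Table 1 with:

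> Death from any cause, with no earlier iPFS event under the other rows of this table, before any new anticancer therapy, and with fewer than two consecutive disease assessments missed immediately beforehand. Date: date of death. Outcome: Event.

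In section 5.3.3.5, state that the same row applies to iDOR, with earlier iDOR event in place of earlier iPFS event.

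Leave the other rows as they are. It may be tempting to add that a reverted iUPD is ignored throughout the table, but that goes too far. A subject who was not clinically stable at iUPD is now an event at that iUPD, and scanning continues after treatment stops (protocol section 4.1). A later iSD reading would then delete an event under a row that is not defective.

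The cost is one table row, one sentence for iDOR and the matching programming. iPFS and iDOR may become slightly less favourable. If the sponsor intends a different reading of the death row, the SAP should state it.

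### SAP Table 1 gives conflicting or premature iPFS and iDOR outcomes for cohort 9 subjects whose iUPD comes directly after two or more missed scans

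*SAP*

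**What the plan says.** SAP 5.3.3.4 defines the iPFS event as the "first iUPD which is subsequently confirmed per iRECIST (iCPD) as assessed by investigator or death due to any cause whichever comes first". Table 1 then assigns an outcome to each situation. Below, its nine rows are numbered in printed order, and *gap* means two or more assessments missed in a row.

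- Row 2 (death) and row 3 (confirmed progression) are events that exclude a gap. Row 3 reads "Documented iCPD (confirmed progression) before subsequent anticancer therapy and not after two or more consecutive missed assessments".
- Rows 4 to 6 make an iUPD an event at its own date: "Documented iUPD and the subject is not clinically stable to continue on treatment"; "Documented iUPD without subsequent scans before subsequent anticancer therapy and the subject is no longer in response follow-up"; "Documented iUPD and all subsequent assessments are iUPD(s) or NE(s) and the subject is no longer in response follow-up". None mentions a gap.
- Row 7, "None of the above and subsequent anticancer therapy started", censors at the last assessment before the new therapy.
- Row 8, "Death or documented iUPD right after two or more consecutive missed disease assessments", censors at the last assessment before the gap.
- Row 9 is the residual row and censors at the last assessment on study.

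SAP 5.3.3.5 applies the same rules to iDOR. For RECIST 1.1 PFS, SAP 5.2.3 censors any PD or death that directly follows such a gap (the bullet names DOR, evidently a copying slip). Protocol 7.1.3 states: "If iUPD is not confirmed at the next assessment, then the appropriate response will be assigned". That response can be iSD, iPR or iCR.

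**The concern.** The gap condition appears in the death and iCPD rows but not in the three iUPD rows, while row 8 catches every iUPD that directly follows a gap. Three problems follow for subjects with that course.

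1. One subject can satisfy an event row and a censoring row at once, with dates months apart and no stated order.
2. Row 8 does not ask whether the iUPD was later confirmed. A subject whose post-gap iUPD resolves has not progressed under iRECIST, yet is censored before the gap and loses all later progression-free follow-up. Retaining such subjects is the reason for analysing by iRECIST.
3. If new therapy also starts, rows 7 and 8 can both apply and give different censoring dates.

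In an open-label single-arm cohort, a choice between event and censoring should not be left to programming after the data are visible.

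**Working it through.** The plan gives no numerical figure for iPFS or iDOR to reproduce, so the check is of the rule logic, followed by dates.

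**Which rows match.** Each course starts with an iUPD directly after a gap.

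| Course | Rows met | Result |
|---|---|---|
| A. Not clinically stable | 4 and 8 | event, or censored before the gap |
| B. No later scan, off response follow-up | 5 and 8 | event, or censored before the gap |
| C. Only iUPD/NE later, off response follow-up | 6 and 8 | event, or censored before the gap |
| D. Later confirmed (iCPD) | 8 | censored before the gap |
| D2. Confirmed, then new therapy | 7 and 8 | censored at two different dates |
| E. Later iSD, iPR or iCR | 8 | censored before the gap |
| E2. As E, then new therapy | 7 and 8 | censored at two different dates |

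Without a gap, each course tested met exactly one row: resolved iUPD, row 9; unstable iUPD, row 4; confirmed iCPD, row 3.

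**Dates.** Inputs are the cohort 9 calendar in Protocol 4.1 (first scan at week 9, then every 42 days; SAP 2.2 still prints 36 days for this interval) and the SAP formula of date minus first dose plus 1. A scan exactly at week w falls on day 7w + 1, and months are days/30.4375, as in SAP 5.2.3.

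Take iSD at week 9, weeks 15 and 21 missed, and iUPD at week 27.

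- Rows 4 to 6: event on day 7 × 27 + 1 = 190, and 190/30.4375 = 6.24 months.
- Row 8: censored on day 7 × 9 + 1 = 64, and 64/30.4375 = 2.10 months.
- Difference: 190 − 64 = 126 days, or 4.14 months.

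Course E, with the iUPD resolving and the last progression-free scan at week 75: row 9 would give day 7 × 75 + 1 = 526, or 17.28 months. Row 8 gives day 64, a loss of 462 days. With a last scan at week 33 or 51 the loss is 232 − 64 = 168 or 358 − 64 = 294 days.

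Course D2, with confirmation at week 33 followed by new therapy: row 7 censors on day 232 and row 8 on day 64, 168 days apart.

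**Effect on the curve.** The number of affected subjects is not given. One subject is 1/40 = 2.5% of the planned cohort. As an assumed illustration, take 40 subjects, exponential iPFS with a 6-month median, and k of the 40 following courses A to C with the dates above. Averaged over 2,000 simulated cohorts, the 12-month iPFS rate is higher under row 8 than under rows 4 to 6 by about 0.8, 1.6, 3.3 and 4.9 percentage points for k = 1, 2, 4 and 6.

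**The case against.** The best defence is that the table is meant to be read from the top down, since rows 7 and 9 both open by excluding what precedes them. That reading gives each subject one outcome, so it removes the double matches. It leaves a worse asymmetry: after the same gap an unconfirmed iUPD (A to C) is an event while a confirmed progression (D) is censored. SAP 5.2.3 makes no such distinction for RECIST PFS. It also does nothing for course E, where row 8 is the only row that applies. And it would date D and D2 differently, although their scans are identical, only because one subject later started new therapy.

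A second defence is that the ADaM specifications may settle the order. The SAP version 4.0 log sends the derivation of two missed consecutive visits there. Those specifications are not among the documents, and the log does not say that they set row precedence.

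Third, the case is narrow, and this stands. iPFS and iDOR are exploratory; the primary confirmed ORR, the RECIST PFS and DOR, and the interim rule do not use Table 1. Protocol 6.6.1 keeps assessments on schedule during dose interruptions, and Protocol 7.1.1 asks for imaging whenever progression is suspected, so gaps should be uncommon.

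Two stronger readings are tempting but not supported. A reader might infer that cohort 9 iPFS and iDOR are contradictory as a whole, or that pseudo-progressors are generally lost. The courses tested without a gap each meet a single row, and a resolved iUPD without a gap or new therapy falls properly to row 9. A reader might also infer, because rows 4 and 6 lack the new-therapy condition that rows 3 and 5 carry, that progression on later treatment would commonly count as an event. Scheduled imaging stops when new anticancer therapy starts (Protocol 4.1 and 7.1.1), so this omission should matter only rarely.

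**Conclusion.** The concern holds for cohort 9 subjects whose iUPD comes directly after two or more missed scans. For them Table 1 gives both an event and a censored outcome (rows 4 to 6 against row 8), censors a later-resolved iUPD before the gap under any row order, and can give two censoring dates when new therapy follows (row 7 against row 8). The missing new-therapy condition in rows 4 and 6 is a minor related omission.

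For one subject the discrepancy can be 4.1 months with a change from event to censored, or about 15 months of lost follow-up. These figures rest on the constructed calendar above. The shift in the 12-month rate rests on the assumed model and on an assumed number of affected subjects. No conclusion about the primary or secondary endpoints follows. The correction is worth making because it is cheap and settles outcomes before the data are seen.

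**What to change.** Amend SAP Table 1 as follows.

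- Rows 4, 5 and 6: add that the iUPD must not directly follow a gap, as rows 2 and 3 already require.
- Rows 4 and 6: add that the iUPD must precede any new anticancer therapy. Row 5 already has such a clause.
- Row 8: limit it to *death, or an iUPD that is later confirmed or that would meet rows 4 to 6 but for the gap, directly after a gap*. The words *but for the gap* are needed; without them the row would refer to event rows that now exclude every such iUPD. An iUPD later followed by iSD, iPR or iCR then no longer triggers row 8. It falls to row 9, or to row 7 if new therapy starts.
- Precedence: state that row 8 prevails over row 7 when the gap comes before the new therapy, so that the earlier censoring date applies.
- SAP 5.3.3.5: state that the same order applies to iDOR.

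The cost is table wording and matching ADaM logic, with no new data.
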